10.2.6 Hematological Evaluation at Baseline

Table 10.2.6.1 Hematology abnormalities at baseline[†]

	S1 (TR)						S2 (RT)						Total					
	All grades		Gr 1		...		All grades		Gr 1		...		All grades		Gr 1		...	
	N	%	N	%	N	%	N	%	N	%	N	%	N	%	N	%	N	%
Anemia																		
Leukopenia																		
Lymphopenia																		
Neutropenia																		
Thrombocytopenia																		

[†]Defined as the last value recorded before or on the date of first infusion.

S1, Sequence 1; S2, Sequence 2; TR, test-reference; RT, reference-test.

Table 10.2.6.2 Median and range for hematology parameters at baseline[†]

	S1 (TR)				S2 (RT)				Total			
Hemoglobin (g/dL)												
N												
Mean, Std., Median, Range												
WBC (10 ⁹ /L)												
N												
Mean, Std., Median, Range												
Lymphocytes (10 ⁹ /L)												
N												
Mean, Std., Median, Range												
...												
N												
Mean, Std., Median, Range												

[†]Defined as the last value recorded before or on the date of first infusion.

S1, Sequence 1; S2, Sequence 2; TR, test-reference; RT, reference-test.

Listing 10.2.6.3 Hematological abnormalities at baseline (grade ≥ 2)

Sequence	Subject	Lab. Test	Examination	Value	Unit	Std. Value	Std. Unit	Grade
			date					

Listing 10.2.6.4 Hematological tests not assessed at baseline

Sequence	Subject	Lab. Test

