*** Permitted windows for assessments before Day 1 of Cycle 1:**

If physical examination, ECOG PS, vital signs, Hematology, Biochemistry-A, Biochemistry-B, CLcr (provided only if serum creatinine levels are above ULN) and Coagulation were assessed >10 days before Day 1 of Cycle 1, the tests must be repeated the day before or the Day 1 (always prior to lubrinezdin infusion).

If pregnancy test was done >7 days before Day 1 of Cycle 1, the test must be repeated the day before or the Day 1 (always prior to lubrinezdin infusion).

A patient should only be treated if eligibility criteria are still met according to assessments performed closest to treatment start.

Permitted windows for assessments after Day 1 of Cycle 1:

A ± 2 -day time window will be allowed for Hematology, Biochemistry-A and CLcr (provided only if serum creatinine levels are above ULN) on Day 8 and Day 15, and for vital signs on Day 8 of Cycle 1.

A -1 day window will be allowed for physical examination, ECOG PS, vital signs, Hematology, Biochemistry-A, and Biochemistry-B, CLcr (provided only if serum creatinine levels are above ULN) and Pregnancy test on Day 1 of Cycle 2 and further cycles (always prior to lubrinezdin infusion).

A $+2$ days window for Day 1 lubrinezdin administration of Cycle 3.

If a drug administration is delayed beyond the permitted protocol window, assessments planned for the original administration day must be repeated on the day the dose is finally administered.

^a Should treatment be administered more than ten days after the screening tests, repeat these tests prior to the first infusion and if clinically indicated. Height needs to be measured at baseline only. BSA will not be reported at the EOT. BSA calculated according to DuBois formula (see [Appendix 4](#)).

^b Any patient having any grade ≥ 3 laboratory abnormalities and/or treatment-related AEs is suggested to have the relevant tests re-assessed at intervals of at least 72 hours but not more than one week until recovery to at least grade 2 has been documented.

^c Repeat during treatment period and at EOT if clinically indicated.

^d Calculated CLcr [Cockcroft and Gault's formula] should be provided only if serum creatinine levels are above ULN.

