5.2 PLANNED STUDY PERIODS (INDIVIDUALLY PER PATIENT)

Patients will be evaluated at scheduled visits in three study periods:

- **Pre-treatment (screening)**: from signature of the ICF to the day of first administration of the study treatment (bosentan or lorbinectedin).
- **Treatment**: from first administration of the study treatment (bosentan or lorbinectedin) to the last dose of lorbinectedin plus 31 days (end-of-treatment, EOT) (maximum of three cycles).
- **Follow-up of adverse events**: after EOT, patients with treatment-related toxicities $>$ grade 2 will be followed every four weeks until recovery to at least grade 1 or stabilization of all treatment-emergent AEs, or until the start of a new antitumor therapy, until the continuation of treatment outside this study under a Compassionate Use Agreement or death, whichever occurs first.

Patients will be considered to be **on-study** from the signature of the ICF to the end of the follow-up period. Patients will be considered to be **on-treatment** for the duration of their treatment and until the day of EOT, immediately before the start of the follow-up period.

An end-of-treatment visit will be performed within 31 days (± 10 days) after administration of the last dose of lorbinectedin, unless the patient dies or starts any new antitumor therapy outside this clinical study, in which case the EOT visit should be performed immediately before the start of the new therapy (ideally the day before or the same day).

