6.4 EVALUATIONS DURING TREATMENT

The following assessments will be done while patient is on treatment ([Table 5](#)). For a more graphic display, please refer to the table [Schedule of Assessments and Procedures](#).

Table 5. Evaluations during treatment.

	ASSESSMENT	TIME
1. Clinical examination	♦ Complete physical examination, including weight and calculation of BSA. ^a	Sequence 1 (TR) and Sequence 2 (RT): Day 1 of each cycle (always prior to lorbinecetin infusion). Also repeat on Day 1 of Cycle 1 (prior to lorbinecetin infusion) if more than ten days have passed since the screening assessment.
	♦ Vital signs: heart rate, blood pressure and body temperature.	Sequence 1 (TR) and Sequence 2 (RT): Day 1 of each cycle (always prior to lorbinecetin infusion), and Day 8 in Cycles 1 and 2. Also repeat on Day 1 of Cycle 1 (prior to lorbinecetin infusion) if more than ten days have passed since the screening assessment.
	♦ ECOG performance status (Appendix 1).	Sequence 1 (TR) and Sequence 2 (RT): Day 1 of each cycle (always prior to lorbinecetin infusion). Also repeat on Day 1 of Cycle 1 (prior to lorbinecetin infusion) if more than ten days have passed since the screening assessment.
2. Laboratory tests ^b	♦ Hematology: Differential WBC (including neutrophils, monocytes and lymphocytes), erythrocytes, hemoglobin, hematocrit and platelets. ♦ Biochemistry A: AST, AP, ALT, lactate dehydrogenase (LDH), creatinine, glucose, creatine phosphokinase (CPK), CPK-MB fraction (if CPK is elevated above the normal range) and gamma glutamyltransferase (GGT) and total bilirubin (direct bilirubin if total bilirubin is above the ULN).	Sequence 1 (TR) and Sequence 2 (RT): Cycle 1: Day 8 and Day 15. Also repeat on Day 1 of Cycle 1 (prior to lorbinecetin infusion) if more than ten days have passed since the screening assessment. Cycle 2: Day 1, Day 8 and Day 15. Cycle 3: Day 1. (always prior to lorbinecetin infusion).
	♦ Biochemistry B: Serum electrolytes (Na+, K+, Mg++), total calcium, total proteins, albumin, CRP.	Sequence 1 (TR) and Sequence 2 (RT): Cycle 2 and Cycle 3: Day 1 of each cycle (always prior to lorbinecetin infusion). Also repeat on Day 1 of Cycle 1 (prior to lorbinecetin infusion) if more than ten days have passed since the screening assessment.

	ASSESSMENT	TIME

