2 OVERALL STUDY DESIGN

This is a prospective, open-label, two-way crossover, phase Ib drug-drug interaction study in patients with advanced solid tumors.

The study will include a pre-treatment (screening) phase (within 14 days before the first lurbinectedin or bosentan administration) followed by a treatment phase consisting of two lurbinectedin cycles, one cycle in combination with bosentan and one cycle of lurbinectedin as single agent (in different order depending on the study sequence), and one additional third cycle of lurbinectedin as a single agent for patients who meet the continuation criteria and obtain a clinical benefit after the first two cycles, and then follow-up of adverse events if any.

Patients who meet the continuation criteria and obtain a clinical benefit according to the Investigator's criteria will have the opportunity to continue treatment under a Compassionate Use Agreement after the completion of the optional third study cycle.

Patients will be treated as outpatients. At the discretion of the Investigator, patients may be admitted to the study center on Day -1 or Day 1 and monitored, at least, until completion of the Day 1 PK blood sample collections.

[figure not shown]
Patients will receive a maximum of three cycles: two consecutive cycles of lurbinecetin, one cycle with and one cycle without bosentan co-administration (in different order depending on the study Sequence 1 or Sequence 2 of treatment), followed by a third cycle with lurbinecetin alone (this last optional for patients with clinical benefit). Lurbinecetin will be administered as a 1-hour (-5/+20 min) i.v. infusion every three weeks (q3wk) via a central or peripheral vein.

In the co-administration cycles, bosentan will be administered orally twice daily in the morning and evening during the prior five consecutive days, self-administered at home from Day -5 to Day -1 (i.e., five days before lurbinecetin infusion), and once daily on Day 1 (i.e., the day of lurbinecetin infusion), following recommendations at the Summary of Product Characteristics (SmPC). On Day 1 (i.e., the day of lurbinecetin infusion), bosentan will be given immediately prior to starting the lurbinecetin infusion. In fact, bosentan should be administered after obtaining the bosentan PK sample #1 and before the start of lurbinecetin infusion (-15 min to -1 min).

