7.1 Baseline and Demographics

Descriptive statistics will be used to summarize the patients' baseline characteristics

Baseline data such as demographics, cancer history, prior therapy, prior relevant history, signs and symptoms, ECG, LVEF, physical examination, vital signs, laboratory values and concomitant medication, coded according to the World Health Organization (WHO) Anatomical Therapeutic Chemical (ATC) classification system, will be described following standard tables (detailed in Section 10, Appendix I).

Age, baseline weight, height and BSA values will be summarized descriptively. Age categories, sex, race and baseline ECOG PS will be summarized with frequency counts.

For the cancer history, times from initial diagnosis, metastatic disease, from locally advanced disease and from last progression before the study entry will be summarized. These time calculations will be shown in months and summarized descriptively. Histology and characteristics of the disease at study entry will be tabulated.

Previous relevant medical history (other than cancer) will be listed.

A frequency tabulation of the number of patients with the different types of previous surgery, radiotherapy or therapy will be given.

Signs and symptoms will be displayed by tabulation of frequencies according to NCI-CTCAE v.5 toxicity grades. Signs and symptoms will be listed.

In case of pre-treatment characteristics with multiple measurements per subject before the start of treatment (e.g. laboratory assessments or vital signs), the last value prior to or on the first day of treatment will be considered the baseline measurement.

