Notes: Percentage is based on number of patients in total and by sequence, when applicable.

[†]For ALT, AST, AP, GGT, and Bilirubin parameters, worst grade will be calculated compared to baseline.

*Creatinine increased, hyperglycemia, hypoglycemia, CPK increased, GGT increased, bilirubin increased, hypoalbuminemia, hypernatremia, hyponatremia, hyperkalemia, hypokalemia, hypermagnesemia, hypomagnesemia, hypercalcemia, hypocalcemia.

S1, Sequence 1; S2, Sequence 2; TR, test-reference; RT, reference-test.

If a low number of patients with grade ≥ 3 ALT or AST increased, the following table will be omitted and the information will be provided in a listing.

Table 11.4.3.4 Time course for AST and ALT

	BOS+LRB		LRB alone		Total	
	N	Median (range)	N	Median (range)	N	Median (range)
AST (Grade≥ 3)						
Onset day						
Peak day						
Recovery day						
Days of recovery to grade ≤ 2						
ALT (Grade≥ 3)						
Onset day						
Peak day						
Recovery day						
Days of recovery to grade ≤ 2						

BOS, bosentan; LRB, lubirenedin.

If appropriate, inter-cycle time courses for neutropenia, thrombocytopenia or any other significant parameter will be displayed in graphs.

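### The SAP gives two conflicting laboratory baselines for Sequence 1; under the table footnotes, some Sequence 1 baselines would be drawn during the bosentan run-in

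*SAP*

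**What the plan says.** Three places bear on the baseline date.

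- SAP 7.1, for measurements taken more than once before treatment (laboratory tests and vital signs are its examples): "the last value prior to or on the first day of treatment will be considered the baseline measurement".
- The footnotes to the baseline tables in SAP 10.2.6, repeated in 10.2.7 and 10.2.8: "Defined as the last value recorded before or on the date of first infusion".
- Protocol 5.2 runs the treatment period "from first administration of the study treatment", and specifies bosentan or lurbinectedin. SAP section 2 likewise places screening before the first dose of either drug.

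In the bosentan cycle, bosentan is "self-administered at home from Day -5 to Day -1" (SAP section 2). In Sequence 1 that is Cycle 1. Cycle 1 Day 1 laboratory tests are conditional: Protocol 6.4 requires them "if more than ten days have passed since the screening assessment". In that case, per the Schedule of Assessments, "the tests must be repeated the day before or the Day 1".

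Baseline is then used in SAP 11.4.3. Tables 11.4.3.1 and 11.4.3.3 cross the worst on-treatment grade with the baseline grade, by sequence and in total. A note to Table 11.4.3.3 adds: "For ALT, AST, AP, GGT, and Bilirubin parameters, worst grade will be calculated compared to baseline".

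**The concern.** The two rules give the same date in Sequence 2, where lurbinectedin is the first drug given, but different dates in Sequence 1. The SAP does not say which governs, so two programmers following different sections would build different datasets.

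Under the footnote rule, whether a Sequence 1 baseline is on or off bosentan depends only on how old the screening sample happens to be. Any laboratory change produced by the run-in would then be baseline for some patients and post-baseline for others. The effect of bosentan on the safety profile of lurbinectedin is a secondary objective, so the baseline should not contain exposure to bosentan. Adverse event reporting may not recover such a change. Protocol 8.5.1 limits the adverse event form to events after the first infusion, procedure-related events, and significant changes in ongoing baseline conditions.

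**Working it through.** The plan states no figure to reproduce. The check is of definitions and days. Day -k is k days before the infusion on Day 1.

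**Exposure at the repeat sample (Sequence 1).** Bosentan is taken twice daily on Days -5 to -1.
- Sample on Day 1: 5 × 2 = 10 doses already taken.
- Sample on Day -1: at least 4 × 2 = 8 doses already taken.
- If lurbinectedin is delayed and the run-in reaches the permitted seven days: 7 × 2 = 14 doses.

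**Which baseline each rule gives.**

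| Patient | SAP 7.1 with Protocol 5.2 | Footnotes to 10.2.6–10.2.8 |
|---|---|---|
| Sequence 1, screening labs 6–10 days before Day 1 | screening value, before bosentan | screening value, before bosentan |
| Sequence 1, screening labs 11 or more days before Day 1 | screening value, before bosentan | repeat on Day -1 or Day 1, on bosentan |
| Sequence 2 | before bosentan | before bosentan |

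The first row assumes a five-day run-in and no extra sample during it. With a seven-day run-in, the unrepeated, bosentan-free window shrinks to 8–10 days.

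**How readily the repeat is triggered.** Screening labs may be taken up to 14 days before registration (Protocol 4.1). In Sequence 1, bosentan is handed out after registration, between Day -8 and Day -5 (Protocol Table 4). With registration on Day -r, labs can fall r to r + 14 days before Day 1, which is 15 possible days. No repeat is needed on those at or under 10, a count of max(0, 11 − r).

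| Registration | Lab age at Day 1 (days) | No repeat | Repeat required |
|---|---|---|---|
| Day -5 | 5–19 | 6 | 9/15 = 60% |
| Day -6 | 6–20 | 5 | 10/15 = 67% |
| Day -8 | 8–22 | 3 | 12/15 = 80% |
| Day -11 | 11–25 | 0 | 15/15 = 100% |

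These are shares of permitted days. They become probabilities only if labs are spread evenly over the window, which is an assumption; the documents give no distribution. Sites that sample close to registration would see fewer repeats.

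**How many patients.** With 1:1 allocation of eight patients, Sequence 1 has 8/2 = 4. That is a ceiling for the planned sample. Treated patients who are later replaced also stay in the safety population.

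**ECG.** The Cycle 1 Day 1 pre-infusion ECG in Protocol 6.4 carries no ten-day condition, so in Sequence 1 it always follows the run-in. SAP Tables 10.2.5.6 and 10.2.5.7 label the pre-infusion ECG as baseline. Listing 11.6.2.2 shows baseline and Cycle 1 pre-infusion as separate columns.

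**The case against.** The infusion footnote sits only under the baseline description tables. The shift tables carry no baseline date, and SAP 7.1 is the general rule and names laboratory tests. Read with Protocol 5.2, it already gives the right anchor. This stands as far as it goes: that the shift tables absorb a run-in change is one reading of an unresolved conflict. The only explicit date attached to the laboratory tables is still the infusion date. One could also reconcile the two rules by reading the first day of treatment in 7.1 as the infusion day, but that would keep the mixed baselines and contradict Protocol 5.2.

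The infusion anchor can be defended, because the safety population requires lurbinectedin and adverse event recording largely starts at the infusion. That explains the choice but does not make the baselines comparable.

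A reader might infer that every Sequence 1 baseline is on bosentan. The documents do not support that, since the repeat is conditional. A reader might also infer that the bosentan cycle is biased toward looking cleaner. That does not follow either. The shift tables are by sequence and have no bosentan-cycle column. The comparisons by treatment (Tables 11.4.1.1 and 11.4.2.1 and the model in 11.5) carry no baseline-relative note. All dated laboratory values are listed, so in eight patients a run-in change could still be found by hand.

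Nor is Cycle 2 Day 1 in Sequence 2 a clean mirror image. That sample also follows a full lurbinectedin cycle, and the SAP has no explicit rule for which cycle or treatment it belongs to.

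**Conclusion.** The point holds as a conflict between SAP 7.1 and the footnotes to 10.2.6–10.2.8. Under the footnotes, the Sequence 1 baseline mixes pre-bosentan and on-bosentan values according to the age of the screening sample, while Sequence 2 baselines are always bosentan-free. If that baseline is carried into Tables 11.4.3.1 and 11.4.3.3 and the baseline-relative ALT, AST, AP, GGT and bilirubin grades, run-in changes in the affected patients are lost and the sequences cannot be compared on those outputs.

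The reach is limited to descriptive safety tables. The number of patients is unknown, at most the Sequence 1 patients, and the documents give neither the size nor the direction of any effect of the run-in on laboratory values. No claim of directional bias is made. The primary pharmacokinetic analysis does not use this baseline. It is still worth settling before the tables are run, because the choice changes derived data and the remedy is simple.

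**What to change.** 1. In SAP 7.1, the footnotes to 10.2.6, 10.2.7 and 10.2.8, and section 11.4.3, use one definition: the last value before the first dose of any study drug, bosentan or lurbinectedin.
2. Treat Sequence 1 pre-infusion values from Day -1 or Day 1 as post-baseline.
3. State one rule, the same for both sequences, for the cycle or treatment to which a pre-infusion sample taken after the bosentan run-in is assigned.
4. Apply the same baseline to vital signs, weight and ECG, and reconcile Tables 10.2.5.6 and 10.2.5.7 with Listing 11.6.2.2.

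The cost is SAP wording and a derivation. No new data are needed, because screening tests are required for every patient. The downside is an older Sequence 1 baseline, up to about three weeks before infusion: with registration on Day -6, 6 + 14 = 20 days. It would be older still if registration were earlier. Some change unrelated to bosentan could then fall after baseline, so the sample date should be shown beside the value.

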10.2.7 Biochemical Evaluation at Baseline

Table 10.2.7.1 Biochemical abnormalities at baseline[†]

	S1 (TR)			S2 (RT)			Total					
	All grades		Gr 1	...	All grades		Gr 1	...	All grades		Gr 1	...
	N	%	N	%	N	%	N	%	N	%	N	%
ALT increased												
AST increased												
...*												

[†]Defined as the last value recorded before or on the date of first infusion.

*Creatinine increased, hyperglycemia, hypoglycemia, CPK increased, GGT increased, bilirubin increased, hypoalbuminemia, hypernatremia, hyponatremia, hyperkalemia, hypokalemia, hypermagnesemia, hypomagnesemia, hypercalcemia, hypocalcemia.

S1, Sequence 1; S2, Sequence 2; TR, test-reference; RT, reference-test.

Table 10.2.7.2 Median and range for biochemical parameters at baseline[†]

	S1 (TR)	S2 (RT)	Total
ALT (xULN)			
N			
Mean, Std., Median, Range			
AST (xULN)			
N			
Mean, Std., Median, Range			
...			
N			
Mean, Std., Median, Range			

[†]Defined as the last value recorded before or on the date of first infusion.

S1, Sequence 1; S2, Sequence 2; TR, test-reference; RT, reference-test.

Listing 10.2.7.3 Biochemical abnormalities at baseline (grade ≥ 2)

Sequence	Subject	Lab. Test	Examination date	Value	Units	Std. Value	Std. Units	Grade

Listing 10.2.7.4 Biochemical abnormalities not assessed at baseline

Sequence	Subject	Lab. Test

10.2.8 Coagulation Evaluation at Baseline

Table 10.2.8.1 Coagulation abnormalities at baseline[†]

	S1 (TR)						S2 (RT)						Total					
	All grades		Gr 1		...		All grades		Gr 1		...		All grades		Gr 1		...	
	N	%	N	%	N	%	N	%	N	%	N	%	N	%	N	%	N	%
INR increased																		

[†]Defined as the last value recorded before or on the date of first infusion.

If INR increase is observed, check listing of concomitant medication (anticoagulants) in section 13
S1, Sequence 1; S2, Sequence 2; TR, test-reference; RT, reference-test.

Listing 10.2.8.2 INR increased at baseline (grade \geq 2)

Sequence	Subject	Lab. Test	Examination date	Value	Std. Value	Grade

Listing 10.2.8.3 INR not assessed at baseline

Sequence	Subject	Lab. Test

10.2.9 Signs and Symptoms at Baseline

Signs and symptoms refer to any AE with onset date before the first treatment dose.

Table 10.2.9.1 Signs and symptoms at baseline (MedDRA coded)

MedDRA SOC/PT [†]	S1 (TR)		S2 (RT)		Total	
	N	%	N	%	N	%
...						

Notes: Percentage is based on number of patients in total and by sequence, when applicable.

[†]SOC: System Organ Class; PT: Preferred Term

S1, Sequence 1; S2, Sequence 2; TR, test-reference; RT, reference-test.

Table 10.2.9.2 Signs and symptoms at baseline

No. of signs and symptoms per patient	S1 (TR)		S2 (RT)		Total	
	N	%	N	%	N	%
0						
1						
2						
≥ 3						
Total						

Notes: Percentage is based on number of patients in total and by sequence, when applicable.

S1, Sequence 1; S2, Sequence 2; TR, test-reference; RT, reference-test.

Table 10.2.9.3 Summary of signs and symptoms at baseline

No. of signs and symptoms per patient	S1 (TR)	S2 (RT)	Total
N			

No. of signs and symptoms per patient	S1 (TR)	S2 (RT)	Total
Mean, Std., Median, Range			

S1, Sequence 1; S2, Sequence 2; TR, test-reference; RT, reference-test.

Listing 10.2.9.4 Signs and symptoms at baseline (grade ≥ 2)

Sequence	Subject	Sign/symptom	MedDRA Preferred Term	Grade	Onset date	Relationship
<hr/>						

